10.1.4. Elicited Adverse Events

In addition to asked the open ended question regarding AEs, local application site reactions will be assessed by physical examination or querying the patient. These include the appearance of erythema or rash, or patient reported pruritus (itching).

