3.4. Safety of

All components in [REDACTED] solution are either noted within the FDA's Inactive Ingredients Database as safe or have a long history of safe and effective use. The safety of [REDACTED] Isopropyl Alcohol (70% v/v) Solution was demonstrated in the clinical program. Across the

[REDACTED]

4. Study Objectives

The primary efficacy objective of this study is to determine the efficacy of two skin preparation products, [REDACTED] Applicator and a standard of care [REDACTED] Applicator ([REDACTED]) on the rates of SSI.

The primary safety objectives are to determine the rates of skin irritation or allergic reactions attributed to each product and all other AEs.

5. Investigational Plan

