7.5. Interventions (Day 1)

Patients will have the region surrounding the surgical site scrubbed with the assigned product as described in section 6.3.

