7.6. Assessments During the Inpatient Period

During the post-surgical period while the patient is still in the hospital, the surgical site and surrounding area will be examined for signs of infection or other deep incisional infection and if evident, this will be recorded. Local skin reactions (erythema, rash, or pruritus) or other systemic allergic reactions to the investigational product will be recorded. Other AEs will be assessed by asking the patient an open ended question: How are you feeling? If any antibiotics are prescribed for prophylaxis or treatment of an AE, these will be reported. On the day of hospital discharge, all of the above assessments will also be performed. The patient will be given standard discharge instructions and a card with the name of study nurse or doctor to contact in the event of any post-surgical complications. Patients will be scheduled for an examination appointment or possibly to come to the emergency room if any possibly serious complications have occurred.

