The investigator must make an assessment of relationship of the AE to the investigational product based on the following criteria:

Unrelated: The patient did not receive the investigational product, the temporal sequence of the AE/SAE onset relative to administration of the investigational product is not reasonable, or there is another obvious cause of the AE/SAE.

Unlikely: There is evidence of exposure to the investigational product but there is another more likely cause of the AE/SAE.

Possible: There is evidence of exposure to the investigational product, the temporal sequence of the AE/SAE onset relative to administration of the investigational product is reasonable, but the AE/SAE could have been due to another equally likely cause.

Probable: There is evidence of exposure to the investigational product, the temporal sequence of the AE/SAE onset relative to administration of the investigational product is reasonable, and the AE/SAE is more likely explained by the investigational product than by any other cause.

Definite There is evidence of exposure to the investigational product, the temporal sequence of the AE/SAE onset relative to administration of the investigational product is reasonable, the AE/SAE is more likely explained by the investigational product than by any other cause, and the AE/SAE shows a pattern consistent with previous knowledge of the investigational product or investigational product class.

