11.6. Safety Endpoints

11.6.1. Adverse Events

AEs will be coded using the most recent version of the Medical Dictionary of Regulatory Activities (MedDRA) preferred terms and will be grouped by system, organ, and class (SOC) designation by treatment group. The severity, frequency, and relationship of AEs to investigational products will be presented by preferred term by SOC grouping. Listings of each individual AE including start date, stop date, severity, relationship, outcome, and duration will be provided. Each AE (based on preferred terminology) will be counted once only for a given study patient. If the same AE occurred on multiple occasions, the highest severity and relationship to investigational product will be assumed. Thus, study participants are not counted multiple times in a given numerator in the calculation of frequencies for a specific AE. The frequency and severity of skin irritation or allergic reactions at least possibly attributed to each product will also be presented.

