Appendix B. SSI Definitions

Superficial Incisional SSI

Infection involves only skin and subcutaneous tissue of the incision

AND

Patient had at least one of the following:

1. Purulent drainage from the superficial incision
2. Organisms isolated from an aseptically obtained culture of fluid or tissue from the superficial incision
3. Superficial incision that is deliberately opened by a surgeon, attending physician or other designee and is culture-positive or not cultured (note: a culture negative finding does not meet this criterion)

AND

Patient has at least one of the following signs of symptoms of infection:

- a. Pain or tenderness
- b. Localized swelling
- c. Redness
- d. Heat

4. Diagnosis of superficial by a surgeon, attending physician or other designee

Deep Incisional SSI

Infection involves deep soft tissues if the incision (e.g., fascial and muscle layers)

AND

Patient has at least one of the following:

1. Purulent drainage from the deep incision
2. A deep incision that spontaneously dehisces or is deliberately opened by a surgeon, attending physician, or other designee and is culture-positive or not cultured (note: a culture negative finding does not meet this criterion)

AND

Patient has at least one of the following signs or symptoms:

- a. Fever > 38°C
- b. Localized pain or tenderness

3. An abscess or other evidence of infection involving the deep incision that is detected on direct examination, during an invasive procedure, or by histopathologic or imaging test.

Organ/Space SSI

Infection involves any part of the body, excluding the skin incision, fascia, or muscle layers, that is opened or manipulated during the operative procedure

AND

Patient has at least one of the following:

1. Purulent drainage from a drain that is placed in the organ/space
2. Organisms isolated from an aseptically obtained culture of fluid or tissue in the organ/space
3. An abscess or other evidence of infection involving the organ/space that is detected on direct examination, during an invasive procedure, or by histopathologic examination or imaging test.

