10. TABLE, LISTING, AND FIGURE SHELLS

Table 1:	Subject Disposition - All Randomized Subjects.....	14
Table 2:	Demographic and Baseline Characteristics - mITT Subjects.....	15
Table 3:	Demographic and Baseline Characteristics - PP Subjects.....	16
Table 4:	Antibiotic Use Prior to Surgery – mITT Subjects	16
Table 5:	Antibiotic Use Prior to Surgery – PP Subjects.....	16
Table 6:	Surgery – mITT Subjects.....	17
Table 7:	Surgery – PP Subjects	17
Table 8:	Surgical Site Infection – mITT Subjects	18
Table 9:	Surgical Site Infection – PP Subjects	18
Table 10:	Type of SSI – SSI Subjects	18
Table 11:	Characteristics of SSI – SSI Subjects	18
Table 12:	Antibiotic Use During and Post Surgery – mITT Subjects	19
Table 13:	Antibiotic Use During and Post Surgery – PP Subjects	19
Table 14:	Overall Summary of Adverse Events – mITT Subjects	20
Table 15:	Number and Percentage of Subjects with Adverse Events - mITT Subjects.....	21
Table 16:	Summary of Subjects with Adverse Events by Severity and Relationship – [REDACTED]	22
Table 17:	Summary of Subjects with Adverse Events by Severity and Relationship – [REDACTED]	22
Table 18:	Number and Percentage of Subjects with Adverse Events by Maximum Severity - mITT Subjects	23
Table 19:	Number and Percentage of Subjects Adverse Events by Relatedness - mITT Subjects.....	23
Table 20:	Number and Percentage of Subjects with Elicited Adverse Events by Maximum Severity - mITT Subjects	24

Listings

[REDACTED]
[REDACTED]
[REDACTED]
[REDACTED]
[REDACTED]

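### Application-site reactions are elicited on skin that includes the incision, with no rule for telling them from wound signs, and the visible SAP text omits the protocol's summary of product-attributed skin reactions

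*Protocol*

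**What the plan says.** **Objective.** Protocol section 4 states: "The primary safety objectives are to determine the rates of skin irritation or allergic reactions attributed to each product and all other AEs". SAP section 3.1.2 repeats this.

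**Where the product goes.** Protocol section 6.3 applies both products to the incision site, with one applicator covering up to 1126 cm². Section 7.5 says: "Patients will have the region surrounding the surgical site scrubbed with the assigned product".

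**What is elicited.** Section 10.1.4 lists the signs: "These include the appearance of erythema or rash, or patient reported pruritus (itching". They are found by examination or by asking the patient, and Table 3 schedules the elicited questions at both telephone contacts. For inpatients, section 7.6 says: "Local skin reactions (erythema, rash, or pruritus) or other systemic allergic reactions to the investigational product will be recorded". None of these sections gives a rule on location, onset or wound-edge findings.

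**How causes are separated.** Section 10.1.5 has a five-level relationship rating. Unrelated and Unlikely take events with an obvious or more likely other cause. Possible keeps an event that fits the product in time "but the AE/SAE could have been due to another equally likely cause". Section 10.1.3 records a known diagnosis in place of its symptoms. Section 7.7 lists the surgical site and the application-site skin as two inspection targets at an outpatient visit.

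**What is reported.** Protocol section 11.6.1 says: "The frequency and severity of skin irritation or allergic reactions at least possibly attributed to each product will also be presented". SAP section 8.6.1 has no matching sentence. It tabulates elicited events by treatment group, and Table 20 in SAP section 10 is titled "Number and Percentage of Subjects with Elicited Adverse Events by Maximum Severity - mITT Subjects".

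**The concern.** Redness and itch are ordinary findings at a healing incision, and redness is also one of the infection signs in Appendix B (under "Patient has at least one of the following signs of symptoms of infection"). When the same skin is examined for a reaction to the prep, a count of erythema, rash and pruritus mixes up to three sources: product, wound and infection. The objective asks only for the first.

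Two things are at stake.

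- **Each arm's rate.** If wound signs enter the count, both arms look more irritating than the products are, and any product difference is diluted.
- **Recoverability.** If location is not recorded when the sign is seen or reported, an analyst cannot reliably restore it later.

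**Working it through.** **No planned figure to reproduce.** SAP sections 5 and 6 describe a descriptive study with a convenience sample of 200 (100 per arm). The calculations below show only how sensitive a count is to non-product signs.

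**Inputs**
- r, the product reaction rate: 1.9% and 3.2%, the chlorhexidine hypersensitivity figures in Protocol section 3.1. They are a stand-in, because they are not application-site irritation rates and they concern the comparator's ingredient.
- s, the SSI rate: 2% and 15%, the upper class I figure and upper class II figure in Appendix A. The trial mixes both classes, so 15% for a whole arm is an extreme.
- b, non-infectious wound redness or itch: not in the documents; assumed 0 to 50%.
- q, the share of non-product signs that enter the count: not in the documents. q = 1 is an unfiltered count in which every SSI also counts as a reaction; q = 0 is perfect attribution.

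**Formulas**, assuming independence:
- Total = 1 − (1 − r)(1 − sq)(1 − bq)
- Share of counted patients with no product reaction = (Total − r) / Total

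Example with r = 1.9%, s = 2%, b = 0, q = 1: Total = 1 − 0.981 × 0.98 = 3.9%; share = (0.0386 − 0.019) / 0.0386 = 51%.

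| r | s | b | Total, q = 1 | Share, q = 1 | Share, q = 0.1 | Share, q = 0 |
|---|---|---|---|---|---|---|
| 1.9% | 2% | 0 | 3.9% | 51% | 9% | 0% |
| 1.9% | 15% | 0 | 16.6% | 89% | 44% | 0% |
| 3.2% | 2% | 0 | 5.1% | 38% | 6% | 0% |
| 3.2% | 15% | 0 | 17.7% | 82% | 31% | 0% |
| 1.9% | 2% | 10% | 13.5% | 86% | 38% | 0% |
| 1.9% | 15% | 50% | 58.3% | 97% | 77% | 0% |

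With SSI alone, an unfiltered count has a non-product share of 38% to 89%. With one non-product sign in ten passing the filter, the share runs from 6% to 77% over the whole grid. With perfect attribution it is zero.

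**Effect on an arm difference.** Assume product reactions of 2% v 5%, 100 per arm, and the same unfiltered wound background b in both arms. Each observed rate is p = 1 − (1 − r)(1 − b), the difference is 0.03 × (1 − b), and the standard error (SE) is √[(p₁(1 − p₁) + p₂(1 − p₂)) / 100].

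| b | Difference (points) | SE (points) |
|---|---|---|
| 0 | 3.0 | 2.6 |
| 10% | 2.7 | 4.8 |
| 20% | 2.4 | 5.9 |
| 30% | 2.1 | 6.6 |

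**Which count the SAP delivers.** Protocol section 11.6.1 promises a count filtered by relationship (q below 1). By its title, Table 20 is filtered by nothing (q = 1 for whatever was recorded as elicited). SAP Table 19 shows relatedness for adverse events in general. Because each preferred term is counted once per patient, a patient with both erythema and pruritus can appear in two rows. Adding rows therefore does not give the number of patients with any attributed skin reaction.

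**The case against.** A reader might infer that nothing separates product reactions from wound signs, and that the primary safety rate therefore mostly measures surgery and infection. The documents do not support that reading.

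- The objective, the inpatient recording rule in section 7.6 and the summary in section 11.6.1 all refer to reactions to, or attributed to, the product. Unlikely and Unrelated exist for events better explained by the wound.
- Redness of a known SSI should be recorded as the SSI under section 10.1.3. In Appendix B, redness is one of four supporting signs within a single superficial criterion, which also needs an opened incision that is culture-positive or not cultured. It does not follow that an arm with more SSIs must look more irritating.
- Table 4 describes grade 1 and 2 erythema as target lesions, which ordinary wound-edge redness does not resemble.
- The SAP has tables by relationship (16, 17 and 19), and its listings carry relationship. Shell bodies and form fields are not visible, so the Table 20 point rests on its title and the text of section 8.6.1, and a missing location field cannot be proved.
- The background rates above are assumed, and no between-arm test is planned.

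These points rule out the broad reading but leave a gap. Possible still admits an equally likely other cause. The diagnosis rule does not cover ordinary healing, nor does it say what happens to a sign recorded before the SSI was diagnosed. The two inspection targets in section 7.7 apply only if an outpatient visit is scheduled, and they do not help where the two areas are the same skin. Table 4 is a severity scale and not a case definition, and mild or localized itch is grade 1. Telephone reports involve no examination.

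**Conclusion.** The point holds in a limited form. Neither document gives an operational rule for telling a product reaction from wound healing on skin that is both prepped and incised, and the visible SAP text does not carry over the protocol's attributed skin-reaction summary. A count of the Table 20 kind therefore need not answer the stated safety objective and can include a substantial wound or SSI component.

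The size is unknown. The 38% to 89% range rests on stand-in reaction and SSI rates, independence, and every SSI also being counted as a reaction. For the attributed rate, the share depends on background wound signs and on how many pass the relationship rating. The documents give neither, so a large share is possible but not shown. Wound signs that enter both arms equally would mainly inflate both rates and dilute a difference.

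**What to change.** 1. **Restore the attributed summary.** Add to SAP section 8.6.1 the Protocol 11.6.1 summary of skin irritation and allergic reactions at least possibly due to the product, as patients with any such reaction, by arm. Show Table 20 by relationship as well as maximum severity. For repeated events, SAP 8.6.1 keeps only the highest-severity rule; it should also carry the protocol's highest-relationship rule.
2. **Record location.** On the elicited-event form and in the telephone script, record whether the sign is at the incision or drain, or elsewhere on prepped skin. Show the two as separate rows by arm and keep the total. Exclude neither: dropping at-incision findings could remove true product reactions.
3. **Prevent double counting.** State in Protocol 10.1.4 and SAP 8.6.1 that signs of a diagnosed SSI, including those noted before the diagnosis, are not also counted as application-site reactions. This extends the rule in section 10.1.3.

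The cost is one or two form fields, a line in the script and some SAP wording, with no extra visit. Location reported by telephone will be approximate. Item 2 helps only for patients assessed after the field is added; items 1 and 3 can be settled before database lock.

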This study is a 2-arm, randomized, parallel group, single-site study designed to determine the SSI rates within 30-days post-surgery of pre-surgical skin cleansing with [REDACTED] Applicator or [REDACTED] on patients who are planning to undergo clean (class I wound) or clean-contaminated (class II wounds) surgery based on medical chart review will be approached to consent for the study (see [Appendix A](#) for wound classification definitions and types of surgical procedures to be included). After consenting to the study, screening will be conducted to determine patient eligibility. Eligibility will be determined from chart review and conducting any procedures for information not in the medical chart (e.g., signs of infection at the surgical site where an incision will be performed or patient reported allergies to components of the surgical scrubs). Pre-operative data to be collected on electronic case report forms (eCRFs) include patient's demographics, medical history, antibiotics in the last 4 days, and record of planned surgery. Eligible patients will be randomized with stratification by type of surgery (clean versus clean-contaminated) in a 1:1 ratio to receive skin pretreatment with either [REDACTED] Applicator or [REDACTED] and will undergo surgery. A total of 200 patients is planned (100 in each group). The surgical site will be examined for signs of infection and local skin reactions at least once a day during hospitalization, and at discharge. The patient will be contacted by telephone approximately 3-to-5 days post hospital release and at 30-days post the day of surgery. During these telephone contacts, the patient will be asked about signs of local skin or systemic allergic reactions and a general question about how they are feeling to determine if any other AEs may have occurred. If during these queries, the patient reveals any events that may be indicative of an SSI, they will be asked to see a study doctor to determine if an SSI has occurred. If they have visited another doctor for an evaluation, the patient will be asked to provide any relevant medical records to include in the study files. At any time after discharge up to 30 days post-surgery, the patient will be encouraged to call a study nurse or doctor and arrange for a prompt clinical evaluation if an infection is suspected. Study assessments and procedures will be performed as outlined in the Schedule of Assessments ([Table 3](#)).

Table 3: Schedule of Assessments

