8.2. Safety Endpoints

Safety endpoints will be analyzed over the entire treatment and follow-up period.

- AEs (including specifically local application site reactions and allergic reactions)

9. Safety Monitoring Plan

Safety monitoring will be conducted throughout the study; therefore safety concerns will be identified by continuous review of the data by the PI, clinic staff, clinical monitor, medical monitor, and Zurex.

The IRB, Medical Monitor, PI, Clinical Monitors and Zurex will review any safety concerns throughout the trial. The roles of these individuals are described below.

Medical Monitor: A Medical Monitor has been appointed for the study. The Medical Monitor will be available for making recommendations to the investigator and Zurex on the severity of any SAEs, and the relatedness to the study interventions. The Medical Monitor will also be responsible for tracking and assessing trends in the AEs reported.

Clinical Monitors: The PI will allow representatives of Zurex to periodically monitor, at mutually convenient times during and after the study, all study data. These monitoring visits provide Zurex with the opportunity to evaluate the progress of the study and to obtain information about potential problems. The monitors will assure that submitted data are accurate and in agreement with any medical records or paper source documentation used; verify that investigational products are properly stored and accounted for, verify that patients' consent for study participation has been properly obtained and documented, confirm that research subjects entered into the study meet inclusion and exclusion criteria, and assure that all essential documentation required by Good Clinical Practices (GCP) guidelines are appropriately filed.

Monitors will conduct a site initiation visit prior to the start of the study. At this visit, they will assure that proper study-related documentation exists, assist in training investigators and other site personnel in study procedures and GCP guidelines, confirm receipt of study supplies, and assure that acceptable facilities are available to conduct the study.

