10.1.3. Methods/Timing for Assessing, Recording, and Analyzing Safety Endpoints

AEs will be assessed starting after the first administration of investigational product until the final follow-up at Day 30. General symptoms will be collected via an open ended question: How have you been feeling since the last time we spoke? Elicited AEs will be assessed as described in section [10.1.4](#).

AEs will be documented in the medical/source records, and recorded on the eCRF using accepted medical terms and/or the diagnoses that accurately characterize the event. When a diagnosis is known, the AE term recorded on the eCRF will be the diagnosis rather than a constellation of symptoms. The investigator will assess all AEs for seriousness, relationship to investigational product, and severity. When an event has not resolved by study closure, it will be documented on the AE CRF as “ongoing”.

All AEs, including clinically significant abnormal findings on laboratory evaluations, regardless of severity, will be followed by study physicians until satisfactory resolution (the event either resolved or stabilized and is not expected to resolve in the near term). At the follow-up telephone contact, AEs will be recorded and followed to resolution only if they are serious, or if the study physician assesses them to be clinically significant.

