8.6. Safety Analysis

8.6.1. Adverse Events

AEs will be coded using the most recent version of the MedDRA and will be grouped by SOC and preferred terms designation. The severity, frequency, and relationship of AEs to investigational product will be presented by SOC and preferred term groupings. Elicited AEs will be separately tabulated by treatment group. Listings of each individual AE including start date, stop date, severity, relationship, outcome, and duration will be provided. Each AE (based on preferred terminology) will be counted once only for a given study subject. If the same AE occurred on multiple occasions, the highest severity will be assumed. Thus, study subjects are not counted multiple times in a given numerator in the calculation of frequencies for a specific AE.

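### Protocol 10.1.4 limits elicited AEs to local skin signs although systemic allergic reactions are also sought, and no listed SAP table clearly gives the allergic-reaction rate by arm

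*Protocol*

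**What the plan says.** **What is asked or recorded.** Protocol section 5 (repeated in the synopsis and SAP 3.2) says that at the telephone contacts "the patient will be asked about signs of local skin or systemic allergic reactions", in addition to a general question about how the patient feels. Protocol 7.6, for the inpatient stay, says: "Local skin reactions (erythema, rash, or pruritus) or other systemic allergic reactions to the investigational product will be recorded". Other AEs in that section come from an open question. Protocol 7.7, for outpatient visits, has the application-site skin inspected for signs of allergy and then an open question for other AEs.

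**What counts as elicited.** Protocol 10.1.3 states: "Elicited AEs will be assessed as described in section" 10.1.4. That section covers local application site reactions and then says: "These include the appearance of erythema or rash, or patient reported pruritus (itching". Table 4 in protocol 10.1.5 grades erythema, rash and pruritus and nothing else.

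**What is to be reported.** The primary safety objective (protocol section 4, SAP 3.1.2) is the rates of irritation or allergic reaction due to each product, and of all other AEs. The endpoint in protocol 8.2 and SAP 3.3.2 is "AEs (including specifically local application site reactions and allergic reactions". Protocol 11.6.1 promises the frequency and severity of irritation or allergic reactions with at least a possible attribution to each product. SAP 8.6.1 does not carry that promise over. It says "Elicited AEs will be separately tabulated by treatment group", and the matching shell, Table 20, is titled "Number and Percentage of Subjects with Elicited Adverse Events by Maximum Severity - mITT Subjects".

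**The concern.** The plan describes the actively sought safety events in two ways. One, in the sections on what staff do, includes systemic allergic reactions. The other, in the section that defines the term used by the SAP, does not. The SAP takes up the defined term and drops the one sentence in the protocol that would have produced an allergic-reaction count regardless of the definition.

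The study is descriptive and has no hypothesis test (SAP section 5), so its tables are its result. The protocol itself names hypersensitivity as a disadvantage of chlorhexidine (3.1) and warns of a rare but serious allergic reaction (3.3). If no table is assigned to allergic reactions, the rate has to be assembled afterwards, by choosing preferred terms when the data are already known. With few events, that choice can decide the answer.

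**Working it through.** The plan states no figure on this point, so the check is a comparison of the text.

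1. **Is systemic allergy sought separately from the open question?**
   - Telephone contacts (protocol section 5, SAP 3.2): yes, it is named beside local skin signs and apart from the general question.
   - Inpatient stay (protocol 7.6): yes, it is recorded apart from other AEs.
   - Outpatient visit (protocol 7.7): no, only application-site skin and then the open question.

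2. **Is it within the defined elicited set?** 10.1.3 makes 10.1.4 the governing description. The subject of 10.1.4 is local application site reactions. Its list is open-ended, but only within local reactions, so it does not reach systemic ones. Table 4 fits the narrow reading because it has no row for a systemic reaction.

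3. **Does the SAP widen the set?** No. SAP 8.6.1 uses the term without a definition. On the available text, 10.1.4 is the only definition that Table 20 can draw on.

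4. **Does another listed table give the rate?** SAP section 2 says the document contains all planned analyses. Its 20 table titles compare as follows:

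| SAP tables | Content by title | Allergic-reaction rate by arm? |
|---|---|---|
| 1–13 | Disposition, baseline, antibiotics, surgery, SSI | No |
| 14–19 | All AEs: overall, number and percentage, severity, relationship | Events included, but no title gives an allergy count |
| 20 | Elicited AEs by maximum severity | Not if 10.1.4 applies; rows not available |

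5. **Can the rate be read off Tables 14–19?** Only in part. Under 10.1.3 a known diagnosis is entered as one term, so a diagnosed allergic reaction appears as itself. Where no diagnosis is made, the signs are coded as separate preferred terms. Each term is counted once per patient, but a patient can appear under several terms. Adding terms therefore does not give a number of patients.

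6. **Sensitivity to one patient.** With the planned 100 per arm, 1/100 = 1 percentage point. Classifying one patient differently moves that arm's rate by one point.

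**The case against.** The strongest reply is that nothing is lost. Every systemic reaction is an AE, is shown by preferred term, severity and relationship in Tables 14–19, and appears in the individual listings. Protocol 11.6.1 does promise the allergic-reaction presentation. The endpoint says allergic reactions without the word systemic, and protocol 7.7 uses allergy for application-site skin, so part of the allergic component already falls within erythema, rash and pruritus. Table 4 even grades rash over more than 30% of body surface and widespread pruritus. All of this stands, and it limits the point to a missing dedicated count. It does not supply that count: a promise in the protocol that the SAP leaves out has no table assigned to it.

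Four stronger readings are tempting, but the documents do not support them.

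- **That Table 20 definitely excludes systemic reactions.** Only its title is available. Its rows, and the footnote attached to the schedule row for elicited AE questions, are not in the text, so this remains an inference from 10.1.4.
- **That a missed case is very likely.** Protocol 3.1 cites hypersensitivity in 1.9% of women and 3.2% of men. Applied to 100 patients, 1 − (1 − 0.019)^100 = 0.853 and 1 − (1 − 0.032)^100 = 0.961. Those rates are not for systemic-only reactions, and patients with known allergy to the components are excluded (7.3.2). The 85–96% chance therefore does not measure this gap.
- **That the signs in protocol 3.3 are what staff ask about.** They are instructions to patients on when to seek emergency help. Some, such as dizziness, are non-specific after surgery, so counting them without a relatedness condition could label ordinary postoperative symptoms as allergy.
- **That the question is already asked at every contact.** Protocol 7.7 is limited to application-site skin and the open question.

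**Conclusion.** The point holds as an inconsistency within the protocol that carries through to the SAP. Section 10.1.4 is narrower than sections 5 and 7.6, and SAP 8.6.1 both inherits the narrow term and omits the 11.6.1 presentation. No listed table clearly delivers the allergic-reaction rate by arm, which is a named part of the primary safety objective and endpoint.

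It is a gap in assigned output and does not mean that data are lost. Its size in patients cannot be given, because the documents contain no rate for systemic reactions alone. The conclusion assumes that Table 20 follows 10.1.4; if its rows already include systemic allergic reactions, what remains is the wording of 10.1.4 and 7.7 and the missing relatedness-based presentation. The change should be made because the objective is explicit and the repair is small.

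**What to change.** **Protocol.** Reconcile 10.1.4 and 7.7 with sections 5 and 7.6 so that elicited AEs comprise local application-site reactions and systemic allergic reactions.

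**SAP 8.6.1.** Restore the protocol 11.6.1 analysis, either as its own table or as rows in Table 20. By treatment group, give the number and percentage of patients with:

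- any local application-site reaction;
- any systemic allergic reaction;
- either of these.

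Count only reactions judged at least possibly related, and count each patient once per row whatever the number of preferred terms. Keep Table 4 for local reactions and use the general AE severity scale in protocol 10.1.5 for systemic ones, stating in the table which scale applies to which row. Fix the list of preferred terms before database lock; protocol section 11 already requires the SAP to be final by then.

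**Cost.** A few sentences in the protocol, one paragraph in the SAP, three table rows and an agreed term list. Outpatient visits would need the allergy question made explicit. The main downside is that the term list has to be settled in advance; the systemic row will also rest on very few events, so it should be read as a count and not as a precise comparison between products.
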